4.2.4 Operative complications

In hospital and 30 day morbidity and mortality will be prospectively monitored.

5.0 TOXICITIES, DOSE MODIFICATIONS, AND MANAGEMENT:

Adverse events should be coded according to CTCAE version 4 (Appendix C).³⁸

5.1 Erlotinib Dose Modification/Toxicity Management

5.1.1 Dose Modifications

Discontinue Erlotinib (TARCEVA) for:

- Interstitial Lung Disease (ILD).

- Severe hepatic toxicity that does not improve significantly or resolve within three weeks
- Gastrointestinal perforation
- Severe bullous, blistering or exfoliating skin conditions.
- Corneal perforation or severe ulceration.

Withhold Erlotinib (TARCEVA):

- During diagnostic evaluation for possible ILD.
- For severe (CTCAE grade 3 to 4) renal toxicity, and consider discontinuation of TARCEVA.
- In patients without pre-existing hepatic impairment for total bilirubin levels greater than 3 times the upper limit of normal or transaminases greater than 5 times the upper limit of normal, and consider discontinuation of erlotinib (TARCEVA.).
- In patients with pre-existing hepatic impairment or biliary obstruction for doubling of bilirubin or tripling of transaminases values over baseline and consider discontinuation of erlotinib (TARCEVA)
- For persistent severe diarrhea not responsive to medical management (e.g., loperamide).
- For severe rash not responsive to medical management.
- For keratitis of (NCI-CTC version 4.0) grade 3-4 or for grade 2 lasting more than 2 weeks.
- For acute/worsening ocular disorders such as eye pain, and consider discontinuation of erlotinib (TARCEVA).

Reduce Erlotinib (TARCEVA) by 50 mg decrements:

- If severe reactions occur with concomitant use of strong CYP3A4 inhibitors [such as atazanavir, clarithromycin, indinavir, itraconazole, ketoconazole, nefazodone, nelfinavir, ritonavir, saquinavir, telithromycin, troleandomycin (TAO), voriconazole, or grapefruit or grapefruit juice] or when using concomitantly with an inhibitor of both CYP3A4 and CYP1A2 (e.g., ciprofloxacin). Avoid concomitant use if possible.
- When restarting therapy following withholding treatment for a dose-limiting toxicity that has resolved to baseline or grade ≤ 1 .

Drugs Affecting Gastric pH

- Avoid concomitant use of erlotinib (TARCEVA) with proton pump inhibitors if possible. Separation of doses may not eliminate the interaction since proton pump inhibitors affect the pH of the upper GI tract for an extended period.
- If treatment with an H₂-receptor antagonist such as ranitidine is required, erlotinib (TARCEVA) must be taken 10 hours after the H₂-receptor antagonist dosing and at least 2 hours before the next dose of the H₂-receptor antagonist.
- Although the effect of antacids on erlotinib pharmacokinetics has not been evaluated, the antacid dose and the erlotinib (TARCEVA) dose should be separated by several hours, if an antacid is necessary.

6.0 SCHEDULE OF EVALUATIONS / STUDY CALENDAR:

6.1 Schedule of Evaluations

Parameter	Pre-study	Neoadjuvant Erlotinib Q 2wks*** (D1,15,29,43)	Neoadjuvant Erlotinib (D57)	Surgery (within 4-6 weeks from PET/CT scan)	Post-Surgical Follow up ^b	End of Treatment Visit	FU**
History	X	X	X		X		X
Physical examination	X	X	X		X	X	X
Weight	X	X	X		X	X	X
Vital signs	X	X	X		X	X	X
Performance status (ECOG)	X	X	X		X	X	X
CBC, differential, platelet count	X	X	X		X	X	X
, LFTs, Cal, Mg, ^A	X	X	X		X	X	X
Serum HCG ^A	X						
PFTs ^B	X						
AE Evaluation		X	X		X	X	
CT scan chest or total body PET/CT Scan and CT Scan or MRI of Abdomen or total body PET/CT Scan ^c	X		X				Every six month for first year then yearly till 5 years
PET/CT Scan ^d	X		X				
MRI of Brain or CT of Head with contrast [*]	X		If clinically indicated				If clinically indicated
Mediastinoscopy/ EUS/EBUS ^g	X		If clinically indicated###				
Surgical Evaluation	X		X				
Operative & Surgical pathology report					X		
Perioperative morbidity form					X		
EKG ^f	X						
Pill diary		X	X				

^A -Pre-enrollment laboratory tests should be performed within 14 days of study entry. HCG is required only for patients who are women with childbearing potential and must be done within 72 hours prior to start of study drug administration.

^B - PFTs within 8 weeks of study entry

^C - CT Scan of the chest or Pet Scan within 28 days of study entry and a CT Scan or MRI of abdomen through the Liver within 28 days of study entry

*An MRI of the brain with contrast or Head CT Scan within 28 days of study entry

- ^d-PET/CT scan within 6 weeks of study entry is highly recommended and required for operable patients. If a PET scan is performed then a bone scan is not required.
- ^f- EKG within 6 weeks of study entry.
- ^g- Mediastinoscopies are highly recommended for documentation of N2 disease. EUS or EBUS may substitute mediastinoscopy in appropriate clinical setting.
- h- Subjects who do not receive surgery will have an end of treatment visit 30 days (± 3 days) after Post-Treatment Visit.
- **Follow for survival and recurrence every 3 months for first year, every 6 months afterward and document on follow up form.
- *** specified dates +/- 2 working days
- ## required for patients with non-progressive disease NOT undergoing surgery.

7.0 RESPONSE ASSESSMENT:

7.1 Eligibility

RECIST 1.1 will be used for tumor measurements after neoadjuvant erlotinib.⁴¹

Only patients with measurable or evaluable disease at baseline will be included:

Measurable disease - the presence of at least one measurable lesion. If the measurable disease is restricted to a solitary lesion, its neoplastic nature should be confirmed by cytology/histology.

Measurable lesions - lesions that can be accurately measured in at least one dimension with longest diameter ≥ 20 mm using conventional techniques or ≥ 10 mm with spiral CT scan.

Non-measurable lesions - all other lesions, including small lesions (longest diameter < 20 mm with conventional techniques or < 10 mm with spiral CT scan), i.e., bone lesions, leptomeningeal disease, ascites, pleural/pericardial effusion, inflammatory breast disease, lymphangitis cutis/pulmonis, cystic lesions, and also abdominal masses that are not confirmed and followed by imaging techniques; and.

- All measurements should be taken and recorded in metric notation, using a ruler or calipers. All baseline evaluations should be performed as closely as possible to the beginning of treatment and never more than 4 weeks before the beginning of the treatment.
- The same method of assessment and the same technique should be used to characterize each identified and reported lesion at baseline and during follow-up.
- Clinical lesions will only be considered measurable when they are superficial (e.g., skin nodules and palpable lymph nodes). For the case of skin lesions, documentation by color photography, including a ruler to estimate the size of the lesion, is recommended.

7.2 Methods of Measurement

- CT and MRI are the best currently available and reproducible methods to measure target lesions selected for response assessment. Conventional CT and MRI should be performed with cuts of 10 mm or less in slice thickness contiguously. Spiral CT should be performed using a 5 mm contiguous reconstruction algorithm. This applies to tumors of the chest, abdomen and pelvis. Head and neck tumors and those of extremities usually require specific protocols.
- Lesions on chest X-ray are acceptable as measurable lesions when they are clearly defined and surrounded by aerated lung. However, CT is preferable.
- When the primary endpoint of the study is objective response evaluation, ultrasound (US) should not be used to measure tumor lesions. It is, however, a possible alternative to clinical measurements of superficial palpable lymph nodes, subcutaneous lesions and thyroid nodules. US might also be useful to confirm the complete disappearance of superficial lesions usually assessed by clinical examination.
- The utilization of endoscopy and laparoscopy for objective tumor evaluation has not yet been fully and widely validated. Their uses in this specific context require sophisticated equipment and a high level of expertise that may only be available in some centers. Therefore, the utilization of such techniques for objective tumor response should be restricted to validation purposes in specialized centers. However, such techniques can be useful in confirming complete pathological response when biopsies are obtained.
- Tumor markers alone cannot be used to assess response. If markers are initially above the upper normal limit, they must normalize for a patient to be considered in complete clinical response when all lesions have disappeared.
- Cytology and histology can be used to differentiate between PR and CR in rare cases (e.g., after treatment to differentiate between residual benign lesions and residual malignant lesions in tumor types such as germ cell tumors).

7.3 Baseline documentation of “Target” and “Non-Target” lesions

- All measurable lesions up to a maximum of five lesions per organ and 10 lesions in total, representative of all involved organs should be identified as **target lesions** and recorded and measured at baseline.
- Target lesions should be selected on the basis of their size (lesions with the longest diameter) and their suitability for accurate repeated measurements (either by imaging techniques or clinically).

- A sum of the longest diameter (LD) for *all target lesions* will be calculated and reported as the baseline sum LD. The baseline sum LD will be used as reference by which to characterize the objective tumor.
- All other lesions (or sites of disease) should be identified as *non-target lesions* and should also be recorded at baseline. Measurements of these lesions are not required, but the presence or absence of each should be noted throughout follow-up.

7.4 Response Criteria

Evaluation of target lesions

- * Complete Response (CR): Disappearance of all target lesions
- * Partial Response (PR): At least a 30% decrease in the sum of the LD of target lesions, taking as reference the baseline sum LD
- * Progressive Disease (PD): At least a 20% increase in the sum of the LD of target lesions, taking as reference the smallest sum LD recorded since the treatment started or the appearance of one or more new lesions
- * Stable Disease (SD): Neither sufficient shrinkage to qualify for PR nor sufficient increase to qualify for PD, taking as reference the smallest sum LD since the treatment started

Evaluation of non-target lesions

- * Complete Response (CR): Disappearance of all non-target lesions and normalization of tumor marker level
- * Incomplete Response/
Stable Disease (SD): Persistence of one or more non-target lesion(s) or/and maintenance of tumor marker level above the normal limits
- * Progressive Disease (PD): Appearance of one or more new lesions and/or unequivocal progression of existing non-target lesions (1)

- (1) Although a clear progression of “non target” lesions only is exceptional, in such circumstances, the opinion of the treating physician should prevail and the progression status should be confirmed later on by the review panel (or study chair).

7.5 Evaluation of best overall response

The best overall response is the best response recorded from the start of the treatment until disease progression/recurrence (taking as reference for PD the smallest measurements recorded since the treatment started). In general, the patient's best response assignment will depend on the achievement of both measurement and confirmation criteria

Target lesions	Non-Target lesions	New Lesions	Overall response
CR	CR	No	CR
CR	Incomplete response/SD	No	PR
PR	Non-PD	No	PR
SD	Non-PD	No	SD
PD	Any	Yes or No	PD
Any	PD	Yes or No	PD
Any	Any	Yes	PD

- Patients with a global deterioration of health status requiring discontinuation of treatment without objective evidence of disease progression at that time should be classified as having “symptomatic deterioration”. Every effort should be made to document the objective progression even after discontinuation of treatment.
- In some circumstances it may be difficult to distinguish residual disease from normal tissue. When the evaluation of complete response depends on this determination, it is recommended that the residual lesion be investigated (fine needle aspirate/biopsy) to confirm the complete response status.

8.0 CORRELATIVE STUDIES:

Informed consent must be signed prior to obtaining and/or submission of any materials for the laboratory correlative studies.

8.1 Statement of Hypotheses and Objectives:

The objective of the correlative studies is to identify molecular and cellular makers in the tumor and the skin that will predict either a response or resistance to erlotinib in EGFR mutated tumors. We plan to identify the molecular markers that will predict the rate of mediastinal nodal clearance in stage III NSCLC patients with EGFR mutation.

Based on the literature and our preliminary data, we hypothesize that:

- 1) The polymorphism and baseline BIM expression will predict a response to erlotinib
- 2) Baseline c-met expression and the presence of T790M mutation in pre-treatment tumor specimens will predict resistance to erlotinib
- 3) We expect to see autophagy induction in post-treatment specimens compare to pre-treatment specimens. We plan to correlate the baseline autophagy with either sensitivity or resistance to erlotinib

4) The expression of Epithelial to Mesenchymal Transition (EMT) Markers and sensitivity to erlotinib.

5) The presence of \geq grade 2 skin changes is associated with erlotinib-associated inhibition of pEGFR and immune and inflammatory changes in the skin, which correlate with clinical response and patient survival to erlotinib.

6) *Patients who develop significant skin rashes have more competent T-cell mediated immunity that correlate with better clinical outcome.*

8.2 Background and Rationale (see section 2.0).

8.3 Tissue Requirements and Assays

Although high throughput techniques like microarray and proteomics will allow simultaneous determination of up to thousands of genes and proteins in patients before and after the treatment, it is limited by the need for large amounts of tumor tissues and labored collection. Thus, we will focus on several biomarkers suggested by our and others preclinical studies for erlotinib to predict their clinical response and benefit, and only performed array-based genomic analysis and proteomics in selected patients.

8.3.1 Tissue requirements:

Tumor samples: We will put all efforts to obtain at least the diagnostic tissue blocks for the correlative studies. Tumor tissues will be available from the diagnostic biopsy. Pre- and post-treatment tumor biopsies will be obtained in available patients. The tumors will be embedded in OCT solution or snap frozen in a liquid nitrogen bath. Aliquots of tumors will be fixed in formalin and embedded in paraffin.

Skin samples: Serial 3mm-punch skin biopsies under local anesthesia on the back of upper torso are minimal invasive and can be done within 20 minutes during an outpatient visit. This is required only for all patients enrolled in the study who consent to the biopsy, with or without the presence of grade 2 or above skin rash after initiation of erlotinib. A separate or immediate after clinic visit with the treating physician might be arranged to perform the skin biopsy as needed. These samples (~400 mg) will be snapped frozen immediately in liquid nitrogen, and embedded in paraffin.

Timing of tumor or skin biopsy: Pre-treatment biopsy could be obtained within 2 weeks before initiation of the drug treatment. The onset of skin rashes is usually two weeks in patients and last for at least 24 hours after last dose of erlotinib, Thus we will perform post-treatment skin biopsy during the planned surgical resection for lung cancer OR at the peak of skin rash as per patient and treating physician's discretion.

8.3.2 Tissue resources:

The following tissue resources are allowed to collect tissue samples at the time of initial diagnosis, pre- and post-treatment.

- 8.3.2.1 Formalin-fixed, paraffin-embedded (FFPE) tumor blocks
- 8.3.2.2 Endobronchial brush and wash
- 8.3.2.3 CT-guided core biopsy of tumor
- 8.3.2.4 Punch biopsy of skin
- 8.3.2.5 Peripheral blood

8.3.3 The following assays will be performed:

1. Histological Evaluation
2. DNA isolation and mutational analysis
3. FISH
4. Tissue microarray (TMA) and Immunohistochemistry (IHC)
5. ELISPOT assay

Histological Evaluation: Specimens will be evaluated by routine hematoxylin and eosin (H&E) stain for the following assessments: 1) percentage of variable tumor; and 2) non-neoplastic adjacent normal tissue.

DNA Isolation and Mutational Analyses: Tumor cells will be isolated on sections from FFPE tissue blocks by macrodissection if the slides consist of more than 75% of tumor. If the slides consist of less than 75% of tumor, we will first isolate tumor cells from normal cells on the slide onto a thin polymer film (CapSure LCM Caps, Arcturus, Mountain View, CA) by a PixCell Iie Laser Capture Microdissection (LCM) System (Arcturus, Mountain View, CA). The tumor cells will be dissociated from the film in proteinase K-containing lysis buffer. The 75% is chosen arbitrarily. Our previous experience reveals that we can detect a heterozygous point mutation by direct sequencing if it is present at least at 15% (data not shown). An estimate of 3,000 to 10,000 laser shots using a laser beam of 7.5- μ m diameter will be needed to obtain enough analyzable DNA for at least 10 PCR reactions. As normal controls, DNA isolated from adjacent normal lung tissues either by LCM or by macrodissection (if normal tissues is >75%) will be used.

Genomic DNA will be isolated from tumor samples by the DNeasy tissue kit (Qiagen). Targeted gene segments will be amplified by PCR and the mutation status will be determined by the standard procedures.

Tissue Microarray: The development of tissue arrays allows the evaluation of each of many proteins in many sets of normal and tumor tissues using a single slide for each probe. It provides a powerful way to follow up the candidate protein changes proposed in this study with control of technical variation. We will determine the changes in protein expression on tissue microarray (TMA) by IHC and correlate these altered protein changes with the clinical response to erlotinib. Five- μ m sections of normal and tumor tissues embedded in paraffin will be stained with H&E to identify morphologically

representative area of normal and tumor tissues, from which core biopsies will be taken. The tissue microarray will be done with the Tissue Arrayer (Beecher Instruments, [name]). From each specimen (donor), tissue cores with a diameter of 0.6 or 1.0 mm are punched and arrayed on a blank paraffin block (recipient). The spacing between the centers of two adjacent specimens on the array ranged from 3 mm to 8 mm. Two to three hundred cores could be created within the array block. Then the recipient block is incubated at 37°C oven for 1 hour to soften the paraffin and melt the surface of the block.

Immunohistochemistry (IHC): Tissue arrays containing diagnostic, pre- and post-treatment tumor and normal human NSCLC tissues (as described above) will be cut in 5- μ m sections, deparaffinized, rehydrated, and quenched with 1.5% H₂O₂. For EGFR studies, the slides will be treated with DakoCytomation Target Retrieval Solution (DAKO, Carpinteria, CA) in a steam bath at 95°C for 45 minutes. After equilibration in PBS for 15 minutes, the slides were placed in an autostainer (DAKO, Carpinteria, CA) and stained with antibodies to EGFR (DAKO; 1:100 dilution). Immunoreactivity will be detected using DAKO EnVision methods (DAKO) according to the manufacturer recommended procedures. The activated EGFR is detected using antibodies against the phosphorylated forms of EGFR (p-EGFR). Similar IHC staining will be performed using with antibodies specific for other proteins as described previously.[88] For negative controls, slides will be treated with the same procedure, including antigen retrieval, except for omission of the primary antibodies. The level of expression will be assessed as percentage of positive staining cells, and scored as 0 (0%), +1 (1-25%), +2 (26-50%) and +3 (51-100%) as described before [89]. Cell pellets from human NSCLC cell lines known to be positive or negative for EGFR will be used as positive or negative controls for EGFR expression. Negative controls will also be performed by omission of the primary antibody. A sample of recording IHC results is illustrated in Appendix I.

Human IFN- γ ELISA: We will collect 5 ml of peripheral blood using citrate, EDTA, or heparin as anticoagulant from the patients before and 2 weeks after treatment. Plasma will be collected by centrifuging the blood for 10 minutes at 1000 x g within 20 minutes of collection. The plasma will be stored at $\leq 20^{\circ}\text{C}$ or shipped on dry ice. We will analyze the patient plasma samples for in vitro T-cell function by ELISPOT assay using tumor specific antigens. A positive interferon gamma (IFN- γ) response to a common antigen (such as whole influenza virus or EBV) will be used as a control. The results will be correlated to the skin changes and clinical outcome of the patients.

9.0 PATIENT REGISTRATION:

All patients will be registered through the Clinical Trials Office at Montefiore Medical Center ([contact]) Monday through Friday 9:00am – 5:00pm Eastern Standard Time. Eligibility Checklist and Registration Form with supporting documentation, and the signed Patient Consent Form must be emailed to the clinical trials office at Montefiore Medical Center, [contact] , at the time of registration and prior to patient treatment. Please copy the Montefiore Study and Regulatory Coordinator on this email, as well as the Principal Investigator at Montefiore. E-mail addresses are available at the cover sheet of this protocol document.

[figure not shown]
At the time of registration, all eligibility criteria must be checked. Patients must meet all of the eligibility requirements listed in Appendix B (Eligibility Checklist) (Section 3.0). Patients must not start protocol treatment prior to registration.

It is the treating physician's responsibility to review all data submitted to the Clinical Trials Office for accuracy and completeness and he/she must sign the off study form.

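### Section 8.3.3 specifies plasma for an ELISPOT test of T-cell function under an ELISA heading, so the T-cell part of hypothesis 6 has no valid measurement as written

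*Combined protocol and SAP*

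**What the plan says.** Hypothesis 6 in protocol section 8.1 reads: "Patients who develop significant skin rashes have more competent T-cell mediated immunity that correlate with better clinical outcome". It needs a measure of T-cell competence in each patient.

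The numbered assay list in section 8.3.3 ends with "5. ELISPOT assay". ELISA is not on the list. The paragraph that describes the blood immune assay is nevertheless headed "Human IFN- γ ELISA". Its steps are:

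- Draw: "We will collect 5 ml of peripheral blood using citrate, EDTA, or heparin as anticoagulant from the patients before and 2 weeks after treatment".
- Processing: "Plasma will be collected by centrifuging the blood for 10 minutes at 1000 x g within 20 minutes of collection".
- Handling: the plasma is stored cold "or shipped on dry ice".
- Assay: "We will analyze the patient plasma samples for in vitro T-cell function by ELISPOT assay using tumor specific antigens".
- Control: a positive IFN-γ "response to a common antigen (such as whole influenza virus or EBV) will be used as a control".

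The paragraph closes by saying that the results will be related to skin changes and clinical outcome, which ties it to hypothesis 6.

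**The concern.** Two things disagree. The heading names one assay while the list and the body name another. And the sample that is processed is not one on which the named assay can be run. An ELISPOT well receives living cells, exposes them to antigen and counts those that respond. The paragraph describes collecting the fraction from which cells have been spun out.

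At stake is one correlative question. A site that follows the text literally would store plasma only. Cells from before erlotinib cannot be collected once treatment has begun, so a mismatch found late could not be repaired for patients already treated. Those patients would have given research blood for a test that cannot be performed on what was kept.

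**Working it through.** No arithmetic underlies the finding, and the plan gives no figure to reproduce. The check is to set the relevant sections side by side and ask whether any reading yields a T-cell measurement.

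**1. What the named assay needs.** ELISPOT needs viable, antigen-responsive cells. The paragraph's own control shows this: a response to influenza virus or EBV can come only from cells that are present and able to respond.

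**2. What the paragraph supplies.** It supplies plasma after 10 minutes at 1000 x g, stored cold or sent on dry ice. It contains no step for isolating, counting, preserving or stimulating mononuclear cells. I put no weight on the printed storage temperature, since a minus sign may have been lost when the PDF was read.

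**3. Whether correcting one word is enough.**

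| Reading | Assay result | Does it measure T-cell competence? |
|---|---|---|
| Heading right: ELISA on plasma | Circulating IFN-γ | No. It is a different construct, and the control antigen has no role in unstimulated plasma |
| Body right: ELISPOT on plasma | None that is usable | No. The sample does not fit the assay |
| ELISPOT on cells from the same tube | Antigen-specific responding cells | Yes, but the protocol does not specify it |

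**4. Whether another section fills the gap.**

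- Section 1.3 names serum as a biomarker source and mentions collecting peripheral blood, with no handling of cells.
- Section 2.0 uses pre-treatment blood for BIM polymorphism.
- Section 8.3.2 lists peripheral blood as a resource without a procedure.
- The other assays in 8.3.3 (histology, mutation analysis, FISH, and tissue microarray with immunohistochemistry) do not measure T-cell function.
- The calendar in section 6.1 has no row for correlative blood.
- Section 18 specifies no analysis that uses this assay.

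Nothing supplies viable cells or a second T-cell assay.

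**5. How many patients it can touch.** Section 18.2 sets 19 patients in stage one and 55 in total. With two draws each, the ceilings are 19 × 2 = 38 and 55 × 2 = 110 samples. Both assume that every patient consents and gives both samples. Section 1.3 restricts correlative sampling to those who consent, so the true number will be lower if any decline. By the plan's own figures the trial stops at 19 with probability 68.4% if the true clearance rate is 15%, and 13.3% if it is 30%.

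**The case against.** The best defence is that this is a drafting fault. The opening sentences read like plasma handling for an ELISA, and the next two like an ELISPOT protocol. Two procedures may have been run together, or plasma written where blood was meant. The laboratory may well know what to do. This is plausible, but the text does not say it. Section 15.2 tells participating sites not to change the protocol, and section 18.2 plans four to five further sites, so the written procedure matters.

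Several stronger readings are tempting, and the documents do not support them:

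- **That the cells are thrown away.** The protocol says plasma is collected. It is silent on the rest of the tube. The supportable statement is that no cell retention is specified.
- **That plasma contains no T cells at all.** A few residual cells are possible. The point needs only that they are not a usable viable input.
- **That hypothesis 6 is lost entirely.** Its link between rash and outcome needs no blood. Adverse events are evaluated at the two-weekly visits in section 6.1, and survival is followed. Hypothesis 5 rests on skin biopsies and is also unaffected.
- **That 110 samples are wasted.** That is a ceiling, limited by consent and by the stage-one stop.

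The defence is also right that the consequence is small. This is one of six correlative hypotheses, and section 1.3 already accepts that many patients will lack paired specimens.

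**Conclusion.** The inconsistency is real, and the procedure as written fails. Heading, sample and assay in section 8.3.3 do not fit together, and no choice between the two named assays on plasma gives a measure of T-cell competence. The T-cell component of hypothesis 6 therefore has no valid data source in the current text.

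The size is modest: one component of one correlative hypothesis, in at most 55 consenting patients. The primary endpoint, the two-stage rule and the secondary endpoints do not depend on it. The conclusion is about wording. It does not show that sites have handled samples wrongly. It rests on two premises: that ELISPOT requires viable cells, and that no separate instruction outside the supplied documents provides for them. Even if such an instruction exists, the protocol text would contradict it and should be corrected.

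**What to change.** Amend section 8.3.3, and section 8.1 if needed, so that one assay is named with a sample that suits it. Either option can use the existing draw times.

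- **(a) Keep the T-cell question.** Specify that viable mononuclear cells are retained from the pre-treatment draw and the 2-week draw for ELISPOT, and correct the heading. Before adopting this, the laboratory should confirm that 5 ml in the chosen anticoagulant yields enough cells for the tumor antigens and the control. The documents give no figure for this, so it cannot be assumed. The cost is cell processing and viable storage at every site.
- **(b) Keep plasma.** Run an IFN-γ ELISA, put it on the assay list, delete the ELISPOT and control-antigen text, and restate hypothesis 6 in terms of circulating IFN-γ. The amendment should say openly that this replaces T-cell competence with a different construct. The cost is giving up the T-cell function question.

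Both options change protocol text, so under section 15.2 they need IRB approval of an amendment before use. The change is small. Its benefit is greatest if it is made before further pre-treatment samples are taken.
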